Annex 7. OFT Result Form

Number of KIT's Code	0	1	-	0	0	1
Participant's Code						
Test Methods	1. assisted					
	2. unassisted					
Test result	1. Reactive					
	2. Non-reactive					
	3. Indeterminate					

FINAL

Annex 8. Post-test Survey Questionnaire

KIT Code		0	1	-	0	0	1
Participant Code (First 4 letters, year, month, day)							
Name of OW/PE							
1.	Please write your full name or initials						
2.	How was the clarity of the information about HIV test kit you received/obtained? (Select one answer)	1. Extremely unclear					
		2. Unclear					
		3. Fairly clear					
		4. Clear					
		5. Extremely clear					
3.	When you performed HIV self-testing, was there any person (peer) who assisted you?	1. Yes					
		2. No					
4.	How easy was performing an HIV test using the self-testing kit given? (Select one answer)	1. Extremely difficult					
		2. Difficult					
		3. Fairly difficult					
		4. Easy					
		5. Extremely easy					
5.	What was the reason that prevented you from testing using the test kit provided?	1. Extremely difficult					
		2. Difficult					
		3. Fairly difficult					
		4. Easy					
		5. Extremely easy					
6.	This question only applies for those who underwent the self-testing assisted by OW/PE. How would you rate the given support by OW/PE /contact people who accompanied/contacted you during HIV self-testing? (Select an answer)	1. Extremely unclear					
		2. Unclear					
		3. Fairly clear					
		4. Clear					
		5. Extremely clear					
7.	This question only applies if your test results are negative. How much do you want to take an HIV test regularly after taking this test?	1. Extremely not in favour					
		2. Less in favour					
		3. Fairly in favour					
		4. In favour					
		5. Very in favour					
8.	How was your experience in performing this HIV self-testing (saliva test)?	1. Extremely unpleasant					
		2. Unpleasant					
		3. Fairly pleasant					

		4. Pleasant
		5. Extremely pleasant
9.	How sure are you with the accuracy of this test	1. Very doubt
		2. Less sure
		3. Fairly sure
		4. Sure
		5. Very sure
10.	How was your test result?	1. Positive
		2. Negative
		3. Indeterminate
11.	How much do you want to confirm your test results to the healthcare facilities?	1. Extremely unlikely
		2. Fairly unlikely
		3. Fairly likely
		4. Likely
		5. Extremely likely
12.	How likely are you to recommend your peers to undergo the screening test that you just performed?	1. Extremely unpleasant
		2. Unpleasant
		3. Fairly pleasant
		4. Pleasant
		5. Extremely pleasant
13	How much do you trust the accuracy of the test result	1. Extremely unsure
		2. Fairly unsure
		3. Fairly sure
		4. Sure
		5. Extremely sure
14.	What was your test result?	1. Positive → P.13
		2. Negative → P.14
15.	If you are extremely unlikely or unlikely to visit a healthcare service, what are the reasons?	
16.	What is your opinion regarding this HIV testing method?	
17.	What are your suggestions for HIV self-testing?	
18.	What are your suggestions and comments to improve the procedure of this study?	
Note: directly inputted to the system		

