The study will produce scientifically strong evidence as to whether two alternative models of community HIV screening among FSW (assisted and unassisted) result in (1) increased rates of formal HIV testing at health facilities and (2) increased rates of treatment initiation in districts in which the community screening intervention is added to the existing FSW community outreach model.

Two alternative study protocols are described in this document. The bulk of this document presents a protocol for a community randomized controlled trial (cRCT), which is the preferred research design option. However, due to a delay in procurement of the OraQuick® rapid HIV test kits that are to be used in the study, there may be insufficient time to undertake a full cRCT.¹ Accordingly, a contingency protocol that can be implemented in a shorter period of time is also presented.

6. Study Objectives

The primary objectives of this study will provide answers to the following five (5) questions:

1. Does the proportion of FSW who know their HIV status increased?

¹ All research activities must be completed by 31 December 2020.

2. Does the introduction of community HIV screening among FSW increase the rate of HIV testing at health facilities?
3. Does “assisted” or “unassisted” community HIV screening among FSW result in a larger increase in the rate of HIV testing at health facilities?
4. Does “assisted” and “unassisted” community HIV screening among FSW results in a larger increase in the rate of HIV positive case finding?
5. Does the introduction of community HIV screening among FSW increase the rate of initiation of ART?

The secondary objectives of this study will provide answers to the following two (2) questions:

1. What is the acceptability of community-based self-screening for FSWs participating in this study?
2. What is the satisfaction of FSWs participating in this study towards delivery of community-based self-screening?

B. STUDY DESIGN

1. Design Summary

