A short baseline survey will be conducted at the time of initial outreach contact with FSW during the study period. The purpose of the baseline survey is to collect background information on FSW that may be used to assess whether FSW with different characteristics are more or less amenable to community HIV screening and HIV testing at health facilities. An application will be developed so that the survey can be completed and submitted to a server using mobile phones PL/PE/FSW. The following basic information will be gathered (see draft questionnaires for the baseline and post-test surveys in the annex of this protocol).

- Name (full name/initial)
- Age
- Date of birth

- Test Kit ID Number
- Education
- Marital status
- Age at initiation of sex work
- Number of clients last seven (7) days
- Methods of clients' recruitment (fixed facility, street, internet, online platform)
- Consistency of condom use
- Ever been tested for HIV
- When last time tested
- Ever been diagnosed with an STI (other than HIV)

In addition to these questions, FSW will be asked twelve (12) questions in the short version of anticipated HIV stigma scale (Reinius et al., 2017) designed to measure the extent to which participants anticipated negative intrapersonal and interpersonal consequences were they to contract HIV in the future. During data analysis, we will assess the ability of an index constructed from the data items collected to predict which FSW presented at health facilities for formal HIV testing. This will provide an estimate of the impact of anticipated stigma on HIV testing among FSW in Indonesia.

2. Post-test Survey

A short post-test survey will be conducted after the test has been taken. The purpose of post-test survey is to collect information of the experience of clients using the test kit and to record the test result. Some inquiries will be presented on a scale of 1-5, some inquiries will have binary answers (Yes/No, Reactive/Non-Reactive). The following inquiries will be made:

- The clarity of information being provided (flier or short video), on a scale of 1-5
- The easiness of test procedure, on a scale of 1-5
- Perceived accuracy of the test result, on a scale of 1-5
- The quality of response by the assigned contact person/hotline, on a scale of 1-5
- Clients' acceptance/perception towards the study procedure
- The likelihood of clients to recommend their peers to take the test, on a scale of 1-5
- Test result

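### Three post-test survey items (Q5, Q6, Q12) carry response scales that do not fit their questions, Q14's skips loop, and unassisted users never rate the hotline; this weakens the secondary objectives but does not make them unanswerable

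*Combined protocol and SAP*

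**What the plan says.** Section A.6 sets two secondary objectives: "What is the acceptability of community-based self-screening for FSWs participating in this study" and "What is the satisfaction of FSWs participating in this study towards delivery of community-based self-screening". Section E.2 lists what the post-test survey should collect. The list includes "The likelihood of clients to recommend their peers to take the test, on a scale of 1-5" and "The quality of response by the assigned contact person/hotline, on a scale of 1-5".

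Annex 8 is the questionnaire itself:

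- Q12 asks "How likely are you to recommend your peers to undergo the screening test that you just performed" and offers five options from extremely unpleasant to extremely pleasant.
- Q5 asks "What was the reason that prevented you from testing using the test kit provided" and offers five options from extremely difficult to extremely easy.
- Q6 asks "How would you rate the given support by OW/PE /contact people who accompanied/contacted you during HIV self-testing" and offers five options from extremely unclear to extremely clear. It opens with a filter: "This question only applies for those who underwent the self-testing assisted by OW/PE".
- Q14 asks for the test result, already asked in Q10. Q10 has positive, negative and indeterminate; Q14 has only the first two. Its arrows send positive answers to P.13 and negative answers to P.14.
- Q15 asks women who are unlikely to visit a health service for their reasons.

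A note at the end of the form says that answers are entered straight into the system.

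**The concern.** A five-point code means something only if the labels answer the question. A respondent to Q12 may be answering the stem (how likely) or the labels (how pleasant), and the stored number does not show which. A pleasantness code could then be reported as likelihood to recommend without anyone noticing. For Q5, no reason can be recorded at all.

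Women who take the online unassisted route complete the survey by link (section B.1), so no interviewer is there to notice the mismatch. The same women are given a hotline number, and section C.3 assigns a contact person to each woman approached. Yet the only item on support excludes them.

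At stake are three participant-reported measures (recommendation, barriers, support) and possibly the reasons for not going on to a facility (Q15).

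**Working it through.** No sample-size or power figure bears on this point. The check sets each question beside its options, traces the skips, and maps the items to the objectives and to section E.2.

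**1. Question against options.** Annex 8 has ten five-point items: Q2, Q4, Q5, Q6, Q7, Q8, Q9, Q11, Q12 and Q13.

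| Fit | Items | Count |
|---|---|---|
| Options fit the question | Q2 (clarity), Q4 (ease), Q8 (experience), Q9 and Q13 (accuracy) | 5 |
| Loose but interpretable | Q7 (wish to test regularly, scored by favour), Q11 (wish to confirm, scored by likelihood) | 2 |
| Options do not fit | Q5, Q6, Q12 | 3 |

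5 + 2 + 3 = 10. The three misfits carry complete five-level sets identical to those of Q4, Q2 and Q8 respectively. That pattern suggests copying within the form rather than a table broken in reading.

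**2. Skips.** In the baseline questionnaires (Annexes 4 and 6), P.n denotes question n. Read the same way here:

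- Q14 positive → Q13 → Q14: a loop.
- Q14 negative → Q14: a self-reference.

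Neither arrow leads to Q15, which by its content depends on Q11.

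**3. Section E.2 against Annex 8.** Recommendation is listed as a likelihood; Q12 does not offer one. Contact-person or hotline response is listed without restriction; Q6 restricts it to assisted users. The Q6 stem does mention contact people, but the filter removes the women for whom a remote contact matters most.

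**4. How many women.** Section B.5 plans 761 assisted and 761 unassisted self-screeners: 761 + 761 = 1,522.

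| Defect | Women affected, as planned |
|---|---|
| Q12 scale | up to 1,522 |
| Q6 scale | up to 761 (assisted) |
| No contact/hotline rating | unassisted users who used it, at most 761 |
| Q5 options | only women prevented from testing |
| Q15 not reached | only women unlikely to visit a facility, and only if skips are enforced |

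**5. What remains.** For acceptability: Q4, Q8, Q9/Q13, the open Q16, and the routine counts in section E.3 of women offered, agreeing to and completing screening. For satisfaction with delivery: Q2, Q8 and the open Q16 to Q18. Satisfaction loses more, because Q6 is its only rating of support.

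**The case against.** The strongest reply is that this is proofreading of a form that section E.1 itself calls a draft, with the application still to be developed. A self-referring skip would show up the first time the form was run. Section E.4 also allows paper collection, where a wrong arrow does not block the next question. Q14 costs no result data, since Q10 and the Annex 7 result form both allow indeterminate. Q6 and Q12 run from worst to best, so some ordering may survive the wrong labels. And the satisfaction objective is descriptive; no analysis step in section F compares satisfaction with support between assisted and unassisted users.

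Much of this stands. The loss of Q15 is conditional, and Q14 is a nuisance rather than a loss. Draft status makes correction cheap, but the documents show no corrected version. The ordering argument helps least. An ordered answer to an unknown question cannot be reported as likelihood to recommend, and a woman who answers the Q12 labels merely repeats Q8.

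A reader might infer that the secondary objectives cannot be answered at all, that this survey is their only source, or that four items are lost for all 1,522 women. The documents do not support these readings: other items and the uptake counts remain, and only Q12 among the affected items is addressed to every self-screener. A blanket statement that the hotline rating is missing for 761 women would also go too far, since not every unassisted user will have used it.

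**Conclusion.** The point holds as a minor but real defect. As printed, Q5, Q6 and Q12 do not validly measure barriers, support or recommendation. Q14 is a duplicate with looping skips, and unassisted users have no item for the contact/hotline rating in section E.2. Both secondary objectives are weakened, satisfaction with delivery most; neither becomes unanswerable.

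The size is 3 misfitting scales out of 10 five-point items. The largest group affected is up to 1,522 planned self-screeners, for Q12 alone. This assumes that the form is used as printed and that the planned numbers complete the survey. The loss of Q15 further assumes that the app enforces the skips literally.

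A related gap is that none of the ten steps in section F names the post-test ratings, so corrected labels alone would still leave them without a planned analysis.

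**What to change.** Edit Annex 8 before the app is built:

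- **Q12:** use a scale from extremely unlikely to extremely likely.
- **Q6:** use a scale from very poor to very good. Add a contact/hotline version for unassisted users who used it.
- **Q5:** replace the options with a list of reasons and send it to women who received a kit but report no test. Otherwise drop it, because section E.2 places this survey after the test and few or no respondents would qualify.
- **Q14:** delete it and keep Q10, which has the indeterminate option.
- **Q13:** keep it, since it asks about the accuracy of the result, as section E.2 lists. Drop Q9 if only one accuracy item is wanted.
- **Q15:** trigger it from the two unlikely answers to Q11.

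The cost is a short edit and one test run of the skips. It needs no extra participants or visits. The only added burden is one item for some unassisted users and, if Q5 is kept, a message to women who did not use their kit.
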